# **1.2 Primary Objectives**

To determine whether CESM is non-inferior to breast MRI for breast cancer screening

### **1.3** Secondary Objectives

To determine whether CESM is non-inferior to abbreviated breast MRI for breas screening

# **1.4 Third Objectives**

To determine whether CESM is superior to mammography for breast cancer screening

### **1.5** Fourth objective

To determine patient preference for breast MRI versus CESM for breast cancer screening

# 2. BACKGROUND

### 2.1 Study Disease(s)

The limitations of conventional mammography, with its inability to detect breast cancers in dense breast tissue and subsequent reduced sensitivity, are now well-established and have resulted in new legislation in nearly 50% of US states requiring reporting breast tissue density to patients and recommending supplemental imaging screening with ultrasound and MRI. The decreased sensitivity is especially concerning in the intermediate and high-risk groups (6-11). MRI has become the prime alternative in these groups but has its own limitations including increased false positives associated with unnecessary biopsies and anxiety, increased cost, increased time, and decreased availability at many centers (12). Ultrasound is another, less commonly used alternative as it is associated with even more false positives than MRI, is time intensive, and operator dependent.

CESM is a new imaging tool using a dual-energy technique that has been shown in the diagnostic setting to have increased sensitivity for breast cancer detection relative to conventional 2D imaging and equal sensitivity with improved specificity relative to breast MRI. It was FDA approved for diagnostic imaging in 2011. It requires no additional time relative to conventional 2D imaging other than IV line placement and contrast administration and is overall faster than breast MRI. It is less expensive than breast MRI as it is currently being billed as a diagnostic mammogram and is easier to implement into practice than MRI given that it is simply a software upgrade to commonly used mammography equipment and the staff training is minimal.

Given these benefits, CESM may prove to be useful in the screening setting, where traditional imaging tools including 2D imaging, MRI, and ultrasound have shortcomings. This is especially important for those patients who cannot get the more traditional imaging. However, CESM's value in screening has not yet been established. This will be the first reader study that evaluates CESM's role for screening relative to 2D mammography and MRI.

Abbreviated MRI is a new method of performing MRI in which only the critical sequences of the complete MRI exam are acquired and used for interpretation, shortening the overall time of the exam. The images that are acquired are those that are considered vital for MRI interpretation and preliminary studies have shown that abbreviated MRI has similar performance to routine MRI (13-16). As a result, programs are considering using abbreviated MRI protocols for

abbreviated protocol may replace MRJ in the future, it is important to determine how CESM compares with it as well when considering whether CESM can replace MRJ.

# 2.2 Correlative Studies Background

NIA

# **3. PARTICIPANT SELECTION**

Given that this study involves an FDA approved imaging test that is used in clinical care with a well established risk profile, and does not involve a therapeutic agent or investigational device, informed consent will be performed by any member of the study team, including the study coordinator.

# 3.1 **Prospective Patient Recruitment**

# 3.1.1 Inclusion Criteria:

- Women
- Age > or equal to 30 years
- Recommendation for breast biopsy has been made
- Recommendation for biopsy will result from an imaging work-up originating with a screening exam (mammogram, tomosynthesis, ultrasound, or MRJ) that was within 3 months of biopsy.

# 3.1.2 Exclusion Criteria:

- Men
- Women with implants
- Participants who have a known allergy to contrast media.
- Participants who have a known severe allergic response to one or more allergens, defined as anaphylaxis
- Participants with poor asthma control using the National Heart, Lung, and Blood Institute guidelines as defined by:
- Symptoms > 2 days per week
- Short-term beta agonist use > 2 days per week
- Nighttime awakenings > 2 times per month
- Participants with Renal insufficiency or failure, as determined by GFR calculation. Given that GFR is reported as a range, the majority of the reported range must be 60 mL/min/1.73m^2 GFR must be measured for all patients within 24 hours of the 1magmg exams.

- Participants who are pregnant. Pregnant women are excluded from this study due to the radiation dose from the CT scan and its potential teratogenic effects on the fetus.
- Participants who are breastfeeding are excluded because there is an unknown but potential risk for adverse events in nursing infants secondary to contrast administration in the mother.
- Participants with the following underlying medical conditions: multiple myeloma, myasthenia gravis, dysproteinemias, severe cardiac disease, aortic stenosis, primary pulmonary hypertension, cardiac arrythmia, or severe cardiomyopathy. These underlying medical conditions may make the participant more likely to develop a contrast reaction.

This is based on the ACR contrast manual version 10.3 and hospital policy.

- Participants with a concurrent active illness including, but not limited to, symptomatic congestive heart failure, unstable angina pectoris, cardiac arrhythmia, thyroid storm.
- Participants with thyroid carcinoma or thyroid disease for whom systemic radioactive iodine therapy is part of planned diagnostic work-up or treatment within 2 months following the contrast mammogram study.
- Participants with non-MR compatible objects or implants that would make MRI a contraindication.
- Participants who have a pacemaker, pacer wires, implantable defibrillator, or implanted monitoring device.
- Participants with intracranial clips, metal implants or external clips within 10 mm of the head.
- Participants who have had a metal injury to the eye.

# 3.2 Reader Study

# 3.2.1 Inclusion Criteria:

- CESM and MRI exam performed within 3 months of one another.
- CESM and breast MRI exams must be performed as part of imaging work-up based on a screening exam of any type (mammography, tomosynthesis, ultrasound, and MRI)
- CESM studies will include at least four low energy and four recombined images

(LCC, LMLO, RCC, RMLO).

• MRI exams will include at least fluid sensitive sequence, multi-phase Tl-weighted images

## 3.2.2 Exclusion Criteria:

- Imaging sets with implants.
- Imaging sets in which a biopsy or surgical intervention was performed since the most recent screening exam, prior to acquisition of the study MRI or CESM.
- Imaging sets in which a biopsy was recommended, but biopsy was not performed and 2 year imaging follow-up is not available.

### 3.3 Inclusion of Women and Minorities

Women of all races and ethnic groups are eligible for this trial.

### 4. REGISTRATION

### 4.1 **Prospective Patient Recruitment**

**4.1.1** General Guidelines for DF/HCC Institutions

Institutions will register eligible participants in the Clinical Trials Management System (CTMS) OnCore. Registrations must occur prior to the initiation of study imaging. Any participant not registered to the protocol before study imaging begins will be considered ineligible and registration will be denied.

A member of the study team will confirm eligibility criteria and will complete the protocolspecific eligibility checklist.

Following registration, participants may begin protocol. Issues that would cause treatment delays should be discussed with the Overall Principal Investigator (PI). If a participant does not receive protocol imaging following registration, the participant's registration on the study must be canceled. Registration cancellations must be made in OnCore as soon as possible.

4.1.2 Registration Process for DF/HCC Institutions

DF/HCC Standard Operating Procedure for Human Subject Research Titled *Subject Protocol Registration* (SOP#: REGIST-101) must be followed.

### 4.2 Reader Study

Radiologist readers will be recruited from the local community to participate in the retrospective reader study. Verbal or email affirmation of an interest in participation to the research

# **5. TREATMENT AND/OR IMAGING PLAN**

### 5.1 **Prospective Patient Recruitment**

Patients will be recruited after a biopsy has been recommended. Each enrolled participant will receive both a CESM and MRI exam *prior* to the breast biopsy. If the CESM has already been done as part of standard of care within 3 months, then only the MRI will be performed. If the MRI has already been done as part of the standard of care within 3 months, then only the CESM will be performed. If neither has been performed already, then both exams will be performed prior to the biopsy, to occur within 3 months of each other. All CESM and MRI studies performed will be interpreted by the clinical radiology staff. The participant will be contacted by her referring physician with imaging results, per clinical practice.

### 5.1.1 Pre-Treatment Criteria

- 5.1.1.1 GFR 2:60 per the clinical protocol. If a GFR is not available, then a point of care renal function test will be performed and reviewed on the day of the exam before the patient receives the CESM and/or MRI.
- 5.1.1.2 Negative urine pregnancy test. If the patient is of child-bearing potential, then this will be performed and reviewed on the day of the CESM and/or MRI before the patient receives the exam.

### 5.1.2 Duration of Follow Up

No additional dedicated research visits are necessary. Participants will be followed for 2 years through review of their chart to determine whether they developed breast cancer. Participants without follow-up or death will be considered lost to follow-up.

The deidentified imaging data may be used for future undefined research. This has been included in the informed consent document.

### 5.1.3 Criteria for Taking a Participant Off Study

Participants will be removed from study when any of the following criteria apply:

- Withdrawal of consent for data submission
- Death

The reason for taking a participant off study, and the date the participant was removed, must be documented in the case report form (CRF).

When a participant is removed from protocol therapy and/or is off of the study, the relevant Off-Treatment/Off-Study information will be updated in OnCore

# 6. DOSING DELAYS/DOSE MODIFICATIONS

NIA

## 7. ADVERSE EVENTS: LIST AND REPORTING REQUIREMENTS

#### 7.1 Patient Prospective Recruitment

Adverse event (AE) monitoring and reporting is a routine part of every clinical trial. Given that the contrast mammogram and breast MRI will be acquired according to standard of care techniques without alterations in duration, contrast agent, or contrast type and given that the AE profile for these imaging exams are well established, we will not be capturing AEs for the purposes of analysis. We intend to only capture AEs for those patients who initiate phone calls to our department. Should a patient contact the research team, the Pl or co-investigator will evaluate and decide the best management, to include referring patient to the primary care physician for further management or sending patient to the emergency department.

The following list of reported and/or potential AEs (Section 7.1) and the characteristics of an observed AE (Section 7.2) will determine whether the event requires expedited reporting **in addition** to routine reporting.

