### 7.1.5 Expedited Adverse Event Reporting

Investigators **must** report to the Overall PI any serious adverse event (SAE) that occurs after the initial dose of study treatment, during treatment, or within 30 days of the last dose of treatment on the local institutional SAE form.

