### 7.1.6 DF/HCC Expedited Reporting Guidelines

Investigative sites within DF/HCC will report AEs directly to the DFCI Office for Human Research Studies (OHRS) per the DFCI IRB reporting policy.

	OF/HCC Reportable AEs					
Attribution	Gr. 2 & 3 AE Expected	Gr. 2 & 3AE Unexpected	Gr. 4AE Expected	Gr.4AE Unexpected	Gr. 5 AE Expected or Unexpected	
Unrelated Unlikely	Not required	Not required	5 calendar days#	5 calendar days	24 hours*	
Possible Probable Definite	Not required	5 calendar days	5 calendar days#	5 calendar days	24 hours*	

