7.1.8 Routine Adverse Event Reporting

All Adverse Events **must** be reported in routine study data submissions to the Overall PI on the toxicity case report forms. **AEs reported through expedited processes (e.g., reported to the IRB, FDA, etc.) must** also be reported in routine study data submissions.

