# **11.1 Prospective Patient Recruitment**

11.1.1 Data Reporting

Patients will be registered in the Oncore system. Study patient data will be captured in an institutional RedCap system designed and maintained by the study team.

**11.1.2** Data Safety Monitoring

The DF/HCC Data and Safety Monitoring Committee (DSMC) will review and monitor toxicity and accrual data from this study. The committee is composed of clinical specialists with experience in oncology and who have no direct relationship with the study. Information that raises any questions about participant safety will be addressed with the Overall PI and study team.

The DSMC will review each protocol up to four times a year or more often if required to review toxicity and accrual data. Information to be provided to the committee may include: up-to-date participant accrual; current dose level information; DLT information; all grade 2 or higher unexpected adverse events that have been reported; summary of all deaths occurring with 30 days of intervention for Phase I or II protocols; for gene therapy protocols, summary of all deaths while being treated and during active follow-up; any response information; audit results, and a summary provided by the study team. Other information (e.g. scans, laboratory values) will be provided upon request.

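### Section 7.1 captures adverse events only when a patient telephones, which contradicts the all-AE rule in 7.1.8 and leaves mainly non-serious reactions seen at the imaging visit outside the study data

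*Combined protocol and SAP*

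**What the plan says.** Section 7.1 argues that both exams follow standard technique and have a well-known safety profile, so "we will not be capturing AEs for the purposes of analysis". It then sets the capture rule: "We intend to only capture AEs for those patients who initiate phone calls to our department". The next paragraph of 7.1 takes a different line, saying that "the characteristics of an observed AE (Section 7.2) will determine whether the event requires expedited reporting", on top of routine reporting.

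The later sections are written without any telephone condition:

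- **7.1.5:** investigators must "report to the Overall PI any serious adverse event (SAE) that occurs after the initial dose of study treatment", with a window that runs to 30 days after the last dose.
- **7.1.6:** "Investigative sites within DF/HCC will report AEs directly to the DFCI Office for Human Research Studies (OHRS) per the DFCI IRB reporting policy", with deadlines set by grade, expectedness and attribution.
- **7.1.8:** all adverse events must "be reported in routine study data submissions to the Overall PI on the toxicity case report forms".
- **11.1.2:** the DSMC "will review and monitor toxicity and accrual data from this study". The material that may be sent to it includes "all grade 2 or higher unexpected adverse events that have been reported".

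**The concern.** The word *only* in 7.1 makes a call from the patient the sole way into the AE data. Some of the risks the protocol names can show themselves while the woman is still in the department: 7.1.1 and 7.1.2 place extravasation at the moment contrast is given, and both list allergic-type reactions. A woman who is assessed and treated on the spot may have no reason to ring later.

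Staff therefore have two instructions that cannot both be followed. Under 7.1 they leave such an event off the form; under 7.1.8 they must enter it. Different staff could resolve this differently, and the resulting toxicity data would not be interpretable as a count of what happened. Some of these contrast exposures exist only because of the study: the notes to the study calendar (9.1) provide for exams done purely for research and charged to the grant.

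**Working it through.** The plan states no figure on this point, so the main check is a comparison of the text.

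**1. Route of a non-serious, expected reaction seen by staff, with no later call**

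| Section | Is the event captured or reported? |
|---|---|
| 7.1, capture rule | No, because there was no call |
| 7.1.5 | Not applicable (not serious) |
| 7.1.6 | Not required for expected grade 2 or 3 events |
| 7.1.8 | Yes, mandatory |

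For this event 7.1.8 is the only route into the study data, and 7.1 closes it.

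**2. Route of a serious event seen by staff, with no later call.** Section 7.1.5 requires it to be reported to the overall principal investigator. The 7.1 wording does not fit with that, but the duty in 7.1.5 stands without a call.

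**3. Does another section settle the conflict?**

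- No order of precedence is stated.
- Section 7.1.2 has clinicians on hand to assess and treat reactions, but does not say that the event enters the study data.
- The study calendar (9.1) has no AE row.
- Section 7.1 points to 7.2 for AE characteristics, but 7.2 is the reader study. The characteristics are in 7.1.4. This suggests that the sections were not reconciled with one another.

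**4. Scale, for illustration only**

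Inputs:
- extravasation incidence p = 0.1% to 1.2%, quoted in 7.1.1 for CT power injection;
- n = 82, the accrual target in the table in 12.2;
- n = 78, the prospective cases needed in 1.1.1 (40 + 38).

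Assumptions: the CT range carries over to CESM, and each woman has one CESM injection. Expected events are n × p, and the chance of at least one is 1 − (1 − p)^n.

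| n | p | Expected events | Chance of at least one |
|---|---|---|---|
| 82 | 0.001 | 82 × 0.001 = 0.082 | 1 − 0.999^82 = 7.9% |
| 82 | 0.012 | 82 × 0.012 = 0.984 | 1 − 0.988^82 = 62.8% |
| 78 | 0.001 | 78 × 0.001 = 0.078 | 1 − 0.999^78 = 7.5% |
| 78 | 0.012 | 78 × 0.012 = 0.936 | 1 − 0.988^78 = 61.0% |

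At the accrual target, 82 is the most CESM injections the study would give. Under 1.1.2 and 5.1, a woman with a standard-of-care CESM within 3 months has only the MRI, so the research injections may be fewer.

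For MRI, 7.1.2 gives about 7 in 5,000,000 for serious contrast reactions: 82 × 7/5,000,000 ≈ 0.0001 events. The protocol gives no rate for non-serious reactions to either agent, so none is added here.

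**The case against.** The best defence is that 7.1 means only that AEs will not be actively solicited after the visit. The capture sentence follows the statement that AEs are not collected for analysis, and it leads into instructions for patients who contact the team. The next paragraph speaks of observed events and routine reporting. Limited capture is also a reasoned choice for standard exams with a known profile. This has some force: the rationale justifies having no AE analysis, and none is asked for here. But the sentence restricts capture, not solicitation, and *only* does not fit the softer meaning. If that meaning is intended, the wording should say so.

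Three other counter-arguments stand and limit the point:

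- A reader might infer that the DSMC is owed every AE and SAE and would be deprived of them. Section 11.1.2 does not say so. Its list is of what may be supplied, and its AE item covers reported, unexpected events of grade 2 or higher. Contrast reactions and extravasation are listed as expected, so that item would not normally carry them even with full capture. What remains is that the toxicity data the committee can draw on are restricted at source.
- Not every event would be missed. Section 7.1.1 notes that inflammation after extravasation may take 24 to 48 hours to peak, so some women may well call.
- The low end of the scale calculation is 0.08 events, so there may be no extravasation at all.

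**Conclusion.** The contradiction between 7.1 and 7.1.8 is real, and 7.1 does not fit 7.1.5 or 7.1.6. Its practical reach is narrow: mainly non-serious reactions or extravasations witnessed at the CESM or MRI visit and not followed by a call. On the assumptions shown, the expected number of CESM extravasations is below one across the whole prospective cohort. That figure rests on a CT rate and on accrual stopping at 82, so it indicates scale and is not a forecast.

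Two stronger conclusions are tempting and should not be drawn. One is that SAE reporting depends on the patient calling; 7.1.5 imposes the duty regardless. The other is that reactions would go wholly unrecorded; the documents support only that they would not be captured as study AEs, and say nothing to suggest that they would be missing from the clinical record.

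There is no AE endpoint and no effect on the AUC comparison. The matter should be corrected because it concerns the completeness of safety data and is cheap to settle, but it does not threaten the trial's main result.

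**What to change.** Reconcile 7.1 with 7.1.5, 7.1.6 and 7.1.8 so that one capture rule applies:

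- Remove *only* from the capture sentence in 7.1.
- State that events observed by staff at the study imaging visit are recorded on the AE form, together with events that patients report.
- Keep the statement that AEs are not an analysis endpoint.
- While editing, point the cross-reference in 7.1 to 7.1.4 instead of 7.2.

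The cost is a wording change and a short entry at a visit that already takes place. The downside is slightly more data entry.

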#### 7.1.1 Expected Toxicities for CESM

Risk of toxicity is related to the contrast agent that is administered during the imaging exam. Risks include allergic, allergic-like, or physiologic type of reaction to the contrast agent. There is also the risk for contrast induced nephropathy.

There is also a risk for contrast extravasation at the time of contrast administration. Per the ACR Contrast manual v 10 .3 "the reported incidence of intravenous (IV) contrast media extravasation related to power injection for CT has ranged from 0.1% to 1.2%. Extravasated iodinated contrast media can result in injury to surrounding tissues, particularly to the skin, producing an acute local inflammatory response may not peak for 24 to 48 hours. The vast majority of patients in whom extravasations occur recover without significant sequelae. Only rarely will a lowosmolality contrast media (LOCM) extravasation injury proceed to a severe adverse event."

Common reactions to extravasation include initial swelling or tightness at the injection site, and/or stinging or burning pain. On physical examination, the extravasation site may be edematous, erythematous, and tender. More severe injuries include compartment syndrome, tissue ulceration, and tissue necrosis.

Risk of toxicity is also related to the risk of biologic harm from radiation administered during the exam. However, this risk is non-measurable during the course of this study.

### 7.1.2 Expected Toxicities for MRI

Risk of toxicity is related to the contrast agent that is administered during the imaging exam. Risks include allergic, allergic-like, or physiologic type of reaction to the contrast agent. There is also the risk for contrast-induced nephropathy and nephrogenic systemic fibrosis.

There is also a risk for contrast extravasation at the time of MRI contrast administration. The ACR contrast manual states that "gadolinium-basedMRI contrast media have similar to lower toxicity in comparison to iodinated contrast agents; however, extravasations of these agents usually do not cause severe injury, likely due to the smaller total volumes of contrast material that are injected at MRI."

During the MRI, the subject will receive an injection of a contrast made up of an element called gadolinium. *A* possible side effect is that some people experience nausea, diarrhea and headache. Contrast agents with gadolinium have been known to cause a severe skin disease in people who already have some degree of kidney failure. This is known as Nephrogenic Systemic Fibrosis (NSF). It can cause a widespread stiffening of the tissues in the body. While the precise cause of this disorder remains a mystery, it generally occurs in patients whose kidney function is so limited that they require dialysis. *A* blood test will be taken prior to the MRI in order to determine the subject's kidney function. Known renal problems are reasons to exclude subjects from this study.

The United States Food and Drug Administration (FDA) issued a warning about the risk of brain deposits following repeated intravenous use of gadolinium-

based contrast agents (GBCAs) for MRI. After being administered intravenously, GBCAs are mostly eliminated from the body by the kidneys. Trace amounts of gadolinium, however, may stay in the body long-term and are known to be deposited in the skin, bone, and brain. Recent studies conducted in people and animals have confirmed that gadolinium can remain in the brain after intravenous administration, even in individuals with normal kidney function. Available information at this time does not show any adverse health effects related to the deposits in the brain.

The risk of serious adverse reactions to intravenous MRI contrast agents is very small ( $\sim 7 / 5,000,000$ ). In the unlikely event of an adverse reaction, physician and nursing staff are available to evaluate and if necessary, treat patients. One of the more severe, but extremely rare, risks is that of anaphylaxis (a severe allergic reaction that can cause breathing difficulties and/or low blood pressure). A resuscitation cart is on site with all materials essential for urgent treatment in the unlikely event of an anaphylactic reaction. Finally, the institution has a standard procedure to alert a special team designated to respond to patients with life-threatening emergencies should further assistance be needed.

